Scientific justification	
Delayed neuronal damage following aneurysmal subarachnoid hemorrhage (SAH) is a major cause of mortality and handicap; it implies multiple factors involving delayed ischemia and vasospasm. To date, nimodipine is the only preventive drug known to improve neurological outcome of these patients and is the only pharmacological preventive treatment that is recommended by the European stroke organization. Many other drugs have been tested, with contradictory results; among them, cilostazol, a selective inhibitor of phosphodiesterase 3 (PDE 3), seems to get the more promising results on long-term handicap prevention. Its action includes an antiplatelet effect by increasing the availability of cyclic adenosine monophosphate (cAMP) via its inhibition of PDE 3 which degrades cAMP, thus increasing activity of protein kinase A (PKA) which leads to a downstream effect. In addition, an increase in NO production was observed in human aortic endothelial cells by a PKA-mediated activation of endothelial NO synthase (eNOS), leading to vasodilatation. The antithrombotic effect of cilostazol coupled with this vasodilatory action makes it a widely used treatment for arteriosclerosis obliterans, intermittent claudication, and prevention of a second ischemic stroke. Its action might go beyond this effect for preventing delayed cerebral ischemia following SAH; experimental studies show that cilostazol also attenuates cortical spreading and hydrocephalus, protects vascular endothelial cells and inhibits the proliferation of vascular smooth muscle cells. These numerous neuroprotective effects might explain its effectiveness, with a significative decrease (up to 50%) of unfavorable outcome rate, as described in several meta-analysis while other drugs or interventions focusing on vasospasm seem to fail in improving long-term functional outcome despite improving short-term radiographic results. Unfortunately, all cilostazol studies were conducted in Japan, with patients treated using fasudil, a potent Rho-kinase inhibitor, rather than nimodipine, as recommended by local guideline. Our hypothesis is that adding cilostazol to nimodipine in the acute phase of aneurysmal SAH improves long-term neurological outcome.

Primary objective and assessment criterion	Our hypothesis is that adding cilostazol to nimodipine for 14 days following aneurysmal subarachnoid hemorrhage improves neurological outcome 6-months after SAH, assessed by the modified Rankin scale.
Secondary objectives and assessment criteria	
Functional status evaluated at 6 months:
 
 - MOCA score - Return to work - Activities of Daily Living

	
 - Instrumental Activities of Daily Living In-hospital morbi-mortality: - Length of Intensive Care Unit stay - Length of hospital stay - 28-day mortality 
Strong clinical and radiological predictive events of functional status:
 
 - Delayed cerebral ischemia, defined as the occurrence of focal neurological impairment or a decrease of at least 2 points on the Glasgow Coma Scale, which is not apparent immediately after aneurysm occlusion and not attributable to other causes. - Short term evolution of Angiographically defined vasospasm, defined as a reduction of calibre of proximal cerebral vessels seen on either CT-, MR- or catheter angiography - Cerebral infarcts, defined by a diagnosis of cerebral infarction performed by a CT or MR scan within 6 weeks, or on the latest CT or MRI scan made before death within 6 weeks, or at autopsy, not present on the CT or MRI scan between 24 and 48 h after early aneurysm occlusion and not
Experimental design	Multicentre, double-blinded, randomised, placebo-controlled, parallel-group superiority trial using an adaptive group-sequential design
Population involved	Adult patients admitted to an intensive care unit with subarachnoid hemorrhage caused by a ruptured cerebral aneurysm
Inclusion criteria	
 - Ruptured cerebral aneurysm occurring in the last 96 hours - Aneurysm successfully secured by surgical clipping or endovascular coiling - Consent of the patient or, if not possible, of a family member (emergency clause) - Registration in a national health care system
Non-inclusion criteria	
 - Precritical modified Rankin Scale (mRS) > 2 - Non-aneurysmal SAH - Delayed > 96h admission after first symptoms of SAH - Coma defined by GCS of 3-5 with untreatable aneurysm will be excluded" - Known allergy to cilostazol - Pregnancy - Pre-existing major hepatic, renal, pulmonary or cardiac disease - Concomitant use of one other anti-platelet and/or anticoagulant agent - Tutelage or guardianship
Treatment being tested	
Cilostazol
 
 - Phase III - Oral or enteral by gastric tube administration - Starting in the first 96 hours of occurrence of SAH - 100mg twice daily - For 14 days
Benchmark treatment	
Other procedures added by the research	
Standard of care of SAH patients is not modified by the study, may vary across centres but must include:
 
 - Enteral or IV nimodipine administration - Vasospasm / DCI monitoring and treatment

	
 - Radiological assessment of brain damage by cerebral TDM or MRI at day 10-21 
Face to face interview at 6 months by a clinical research assistant from the investigating centre or coordinating investigating centre.

Risks added by the research	1.1 Level C
Summary of the known and foreseeable benefits and risks for the research participants	
The incidence rate of SAH is high, 10 per 100.000 among which 85% are caused by a ruptured aneurysm: neurological deterioration is frequent during the ICU stay and is mainly due to delayed cerebral ischemia. The most recent meta-analysis showed that cilostazol significantly reduced poor outcome patients with SAH, with an Odds ratio of 0.52 [0.37 – 0.74] for unfavourable outcome (16). Our trial aims to confirm that a 14 days administration of 100 mg twice a day of cilostazol will reduce by 30% long-term disability and cognitive impairment of aneurysmal SAH. If so, our trial might dramatically change the therapeutic management of aneurysmal SAH, as nimodipine did long time ago. Collective benefit is also expected, including the reduction of the length of hospital stay and need for rehabilitation.
 
The study protocol will not interfere with other preventive or curative treatment of DCI and vasospasm, which will be kept to the discretion of the physician in charge.
 
Major secondary effects of cilostazol are arrhythmia, abnormal bleeding, and allergy (frequency not reported). Most frequent adverse reactions are headache (up to 34%), palpitation (up to 10%), and diarrhoea (up to 19%). These side effects are however reported in patients taking cilostazol as a long-term therapy. In previous trial on DCI prevention in SAH, 14 days administration of cilostazol appeared safe since no difference in major adverse events rate was observed between cilostazol and control groups.

Practical procedure	Patients will be included within the first 96 hours after admission and randomly assigned to one of the following groups: the cilostazol group, who will receive cilostazol 100mg orally or by enteral tube two times a day for 14 days, or the control group, who will receive a placebo. This treatment should be started within the first 96 hours after hemorrhage.
Number of subjects chosen	630 patients
Research period	
Inclusion: 42 months
 
Participation: 6 months
 
Total: 49 months

Number of inclusions expected per centre and per month	1.9 patients per centre and per month
Statistical analysis	2 interim analysis planned
Funding source	PHRC
Data Monitoring anticipated	Safety Board Yes

2 SCIENTIFIC JUSTIFICATION FOR THE RESEARCH

2.1 Hypothesis for the research

Delayed vasospasm of major cerebral arteries is considered the main cause of delayed cerebral ischemia (DCI) in patients with subarachnoid hemorrhage (SAH)¹. However, reduction of angiographic vasospasm using intra-arterial vasodilatation or drugs such as clazosentan has not been shown to reduce DCI or long-term disability^{2,3}. These findings have broadened the conceptual view of DCI, by including to vasospasm other factors, such as microthrombosis, microvascular constriction, spreading depolarization and spreading ischemia.

Cilostazol is a selective inhibitor of phosphodiesterase 3 (PDE 3) and antiplatelet agent. Its physiological properties combine multiple mechanisms, including inhibition of both cyclic adenosine monophosphate (cAMP) and upregulation of endothelial NO synthesis. In previous clinical studies, it has been shown to reduce DCI by increasing the release of nitric oxide levels from endothelial cells; by inhibiting the vascular smooth muscle proliferation; by suppressing the adhesion molecule expression on vascular membrane; and by inhibiting the platelet-derived growth factor production⁴⁻⁶.

Our hypothesis is that the preventive administration of cilostazol improves long-term neurological outcome of patients presenting with SAH, by reducing DCI rate through these aforementioned multiple mechanisms.

2.2 Description of knowledge relating to the pathology in question

The incidence rate of subarachnoid hemorrhage (SAH) is approximately 10 per 100,000, among which 85% are caused by a ruptured aneurysm. It accounts for about 5% of all strokes. The mortality rate is 30-50% and delayed cerebral ischemia (DCI) affects about 30% of SAH survivors; the risk of DCI is correlated with the Fisher radiologic score and the World Federation of Neurosurgeons score and contributes to poor outcome, long-term disability and cognitive impairment⁷. The DCI mainly occurs between the 4th and the 10th day after SAH^{8,9}.

To date, only administration of nimodipine, as a preventive strategy of DCI, has been shown to improve long-term neurological outcome^{10,11}. It is therefore widely used, although its efficacy is limited. Its mechanisms of action, as a calcium antagonist, include vasodilatation and antifibrinolytic effect.

Data on curative treatment of vasospasm and DCI shows weak evidence and contradictory results, whether pharmacological or intra-arterial interventions. Therefore, management of these complications differs among intensive care units. However, it always includes close monitoring of clinical deterioration; when it occurs, hypertension therapy, intra-arterial dilatation and sometimes adjuvant therapy such as milrinone are used. If sedation is needed making clinical examination not reliable, monitoring of vasospasm with using transcranial Dopplers, electroencephalographic recordings and perfusion CTscans are performed, although the clinical consequences of a radiological vasospasm, when found, is often a matter of debate.

Despite advances in treatment and care protocols, the mortality and morbidity rate of SAH remains high: up to 40% patients of these adults are unable to return to work and even fewer are able to return to their previous occupations because of neurological impairment¹. Therefore, prevention of DCI remains a major priority.

2.3 Summary of relevant pre-clinical experiments and clinical trials

To date, four randomized controlled trials have assessed cilostazol in improving long-term outcome of adult patients with SAH.

In 2011, Suzuki and al. published the first prospective placebo-controlled study evaluating cilostazol in SAH patients¹². A hundred patients were enrolled: although cilostazol did not significantly decrease the incidence of symptomatic vasospasm (37.3% in the control vs. 22.4% in the cilostazol group, $p = 0.18$) and cerebral infarction (27.5% in control vs. 10.2% in the cilostazol, $p = 0.09$). However, the modified Rankin scale at discharge was significantly improved: 2.6 in controls vs. 1.5 in the cilostazol group, $p = 0.041$.

Senbokuya and al. published a second randomized controlled trial in 2013¹³. In this study, data from 109 patients were analysed. Symptomatic vasospasm, angiographic vasospasm and incidence of new cerebral infarctions were significantly lower in the cilostazol group, respectively 13 vs. 40% $p=0.0021$, 50 vs. 77% $p=0.006$, and 11 vs. 29% $p=0.03$. Nevertheless, no statistically significant difference was found regarding mRS at 1, 3 and 6 months but the cilostazol group tended to have better outcomes defined as an mRS 0-2; at 6 months, 88.9% patients and 74.5% had a good outcome in the cilostazol and placebo groups, respectively $p=0.08$. The number of adverse events in both groups was similar.

Matsuda et al. in 2016 included 148 patients in a randomized placebo-controlled study¹⁴. Occurrence of symptomatic vasospasm was significantly less frequent in the cilostazol group: 10.8 vs. 24.3%, $p = 0.031$, as well as the proportion of patients with poor outcome: 5.4 vs. 17.6%, $p = 0.011$. Multiple logistic analyses showed that cilostazol administration was an independently associated with reduced poor outcome: OR 0.221, 95% CI 0.054–0.903, $p = 0.035$.

Sugimoto et al. in 2018 included 50 cases that were randomly assigned to cilostazol (n=23) and placebo (n=27) groups¹⁵. Among the 48 analysed patients, those from the cilostazol group tended to have a better clinical outcome than those from the control group, according to the eGOS at 6 months after SAH (74% versus 56%). This difference was however not statistically significant (odds ratio 1.437, 95% CI 0.376 to 5.483, $P=0.596$).

These four studies were selected in recent meta-analysis¹⁶, which concluded that cilostazol might be beneficial in SAH patients with an OR of 0.52 [0.37 – 0.74] for unfavourable outcome.

It must be noted that all these studies have been conducted in Japan, have included relatively small cohorts and have administered the fasudil, a potent Rho-kinase inhibitor, instead of the nimodipine.

Our study will be therefore the first to evaluate whether cilostazol, in addition to nimodipine, decreases the rate of long-term disability in a large cohort of patients with aneurysmal SAH.

2.4 Description of the population to be studied and justification for the choice of participants

Adult patients admitted to an intensive care unit (ICU) for an aneurysmal SAH occurred within the last 96 hours.

We decided to include only aneurysmal SAH because of the low incidence rate of DCI and bad outcome in non-aneurysmal SAH. Moreover, we decided to include all stages and grades of SAH. Indeed, previous studies suggested that it might be beneficial for all patients regardless of their severity.

Since we hypothesised that cilostazol will improve the outcome by preventing treatment DCI, it should be started at the early phase of SAH before the risk period for DCI, which begins at day 4.

2.5 Identification and description of the experimental medication or medications

Cilostazol is a selective inhibitor of phosphodiesterase 3 (PDE 3) and antiplatelet agent. It is available in a tablet form and can be administered orally or through a gastric tube after being crushed.

"CASH" protocol, version 2.1 of 04/04/2025

2.6 Description and justification of the dosage, administration method, administration design and treatment period.

Patients will be included within the first 96 hours after SAH onset and randomly assigned to either cilostazol or placebo group. The dose of cilostazol will be 100mg twice a day for 14 days,.

The dosage of cilostazol is similar to the one tested in the four previous trial that documented benefit¹²⁻¹⁵.

Pharmacokinetics justification

We reviewed ten human studies that have directly quantified cilostazol's pharmacokinetics under varied dosing and design protocols. In healthy volunteers—primarily Korean subjects—one study reported an AUC of $12,100 \pm 4,880 \text{ ng}\cdot\text{h}/\text{ml}$, while Cmax values ranged from 283.7 to 1,623.9 mg/ml over doses from 25 to 300 mg. Elimination half-life consistently approximated 11 hours, and Tmax varied between 2.4 and 4 hours; one report estimated apparent clearance (CL/F) at 12.8 l/h.¹⁷⁻²⁶

Genetic analyses indicate that CYP3A5 and CYP2C19 variants significantly affect clearance and half-life, whereas ABCB1 appears to have no effect, overall the variance explained by polymorphism was 7% underlining a relevant but limited effect of genetics on cilostazol pharmacokinetics. A study in subjects aged 50 and older found no significant influence of age or gender. Investigations of drug interactions reveal no notable pharmacokinetic change when cilostazol is co-administered with probucol, but co-administration with simvastatin increases simvastatin AUC by 64% and its active metabolite by 31%. The drug will be delivered in oral form if patient is able to swallow the tablet. If not, tablets will be crushed by the nurse in charge of the patient, and given by oral or enteral route through feeding tube if required. Administration of crushed tablet will be standardized at specific timing in each center. In case a patient can eat a meal, the delay between administration and meal will be of 30 minutes minimum

Based on the available data in healthy human studies, the most common cilostazol dose across studies was 100 mg, administered either as a single dose or twice daily. Several studies used this dosing regimen:

- Single 100 mg doses were used in studies by Choi and Kim^{17,18}
- Multiple 100 mg twice-daily doses were used in studies^{19,20}
- Some studies also investigated 50 mg doses^{21,22} or a range of doses. One dose-escalation study examined doses from 25 mg to 300 mg²³.

The most common route of administration was oral, and for multiple-dose studies, the typical regimen was twice daily (BID) dosing^{19,24}.

Dosage in SAH

More specifically on subarachnoid hemorrhage, the dose of **100 mg twice daily for 14 days** was chosen based on **previous clinical trials** evaluating cilostazol in subarachnoid hemorrhage (SAH) patients. Specifically:

- Previous randomized controlled trials (RCTs) in Japan, such as those by **Suzuki et al. (2011)**, **Senbokuya et al. (2013)**, **Matsuda et al. (2016)**, and **Sugimoto et al.**

(2018), have used this dosage with **documented efficacy in reducing delayed cerebral ischemia (DCI)** and **improving neurological outcomes**.

- Pharmacokinetically, cilostazol is a **phosphodiesterase 3 inhibitor** that **increases cyclic AMP (cAMP), leading to vasodilation and antiplatelet effects**. These mechanisms contribute to its potential protective role in preventing secondary ischemia after SAH.
- Preclinical studies have shown that cilostazol inhibits **vascular smooth muscle proliferation, enhances nitric oxide (NO) synthesis, and reduces microthrombosis**, mechanisms that are relevant in SAH pathophysiology.

Thus, the 100 mg BID dose was selected to match the dosage in prior successful studies while ensuring a **favorable safety profile, for which adverse events are depicted in the section 10**.

2.7 Summary of the known and foreseeable benefits and risks for the research participants

The incidence rate of SAH is high, 10 per 100.000 among which 85% are caused by a ruptured aneurysm: neurological deterioration is frequent during the ICU stay and is mainly due to delayed cerebral ischemia. The most recent meta-analysis showed that cilostazol significantly reduced poor outcome patients with SAH, with an Odds ratio of 0.52 [0.37 – 0.74] for unfavourable outcome¹⁶. Our trial aims to confirm that a 14 days administration of 100 mg twice a day of cilostazol will reduce by 30% long-term disability and cognitive impairment of aneurysmal SAH. If so, our trial might dramatically change the therapeutic management of aneurysmal SAH, as nimodipine did long time ago. Collective benefit is also expected, including the reduction of the length of hospital stay and need for rehabilitation.

The study protocol will not interfere with other preventive or curative treatment of DCI and vasospasm, which will be kept to the discretion of the physician in charge.

Major secondary effects of cilostazol are arrhythmia, abnormal bleeding, and allergy (frequency not reported). Most frequent adverse reactions are headache (up to 34%), palpitation (up to 10%), and diarrhoea (up to 19%). These side effects are however reported in patients taking cilostazol as a long-term therapy. In previous trial on DCI prevention in SAH, 14 days administration of cilostazol appeared safe since no difference in major adverse events rate was observed between cilostazol and control groups.

3 OBJECTIVES

3.1 Primary objective

Our main objective is to show that 100mg twice a day of cilostazol over 14 days improves the modified Rankin scale at 6-months in aneurysmal SAH treated with nimodipine, against placebo (Appendix 1)

3.2 Secondary objectives

Secondary objectives are the functional status assessed at 6 months:

- SubArachnoid Hemorrhage Outcome Tool (SAHOT) Score (Appendix 2)
- MOCA score (Appendix 3)
- Return to work
- Activities of Daily Living (Appendix 4)
- Instrumental Activities of Daily Living (Appendix 5)

And In-hospital morbi-mortality:

- Length of ICU stay
- Length of hospital stay
- 28-day mortality

We will also assess the effects of cilostazol on the occurrence of:

-Delayed cerebral ischemia, defined as the occurrence of focal neurological impairment or a decrease of at least 2 points on the Glasgow Coma Scale, which does not occur immediately after aneurysm occlusion and which is not ascribable to other causes.

-Cerebral artery vasospasm, defined as a reduction of the diameter of the proximal cerebral vessels seen on either CT-, MR- or catheter angiography

-Cerebral infarcts, detected on the CT scan or MRI performed with 6 weeks, (or on the latest CT scan or MRI performed before death within 6 weeks, or at autopsy), but not present on the earlier CT or MRI scan performed between 24 and 48 h after early aneurysm occlusion and not ascribable to other causes

4 WE WILL ALSO MONITOR THE OCCURRENCE OF CILOSTAZOL-RELATED ADVERSE AND SERIOUS ADVERSE EVENT.PLAN FOR THE RESEARCH

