4.1.2 Secondary assessment criteria

The main pitfall of the modified Rankin Scale is the overrating of patients that develop cognitive impairment. We thus chose to assess separately cognitive impairment with using specific scales, including the MOCA, ADL and IADL. The SAHOT (SAH-outcome tool) will be finally assessed, as it has been recently developed and validated but not yet commonly used as the mRS¹⁸.

1. SAHOT score (Appendix 2)
2. MOCA score at 6 months (Appendix 3)
3. Return to work at 6 months
4. Activities of Daily Living (ADL) at 6 months (Appendix 4)
5. Instrumental Activities of Daily Living (IADL) at 6 months (Appendix 5)

Other generic morbidity criterion will be used.

6. Length of Intensive Care Unit (ICU) stay
7. Length of hospital stay
8. 28-day mortality

We will also assess the occurrence of cerebral vasospasm, delayed cerebral ischemia and new cerebral infarction as they represent potential confounding factors. Of note cerebral vasospasm diagnosis will be left to the discretion of physician as the strategy to undergo arterial MR/CT scan or DSA differs widely across centres but interpretation of these exams will be requested to be standardized in all participating centres. As aforementioned, New cerebral infarcts will be considered when detected on the CT scan or MRI performed with 6 weeks, (or on the latest CT scan or MRI performed before death within 6 weeks, or at autopsy), but not present on the earlier CT or MRI scan performed between 24 and 48 h after early aneurysm occlusion and not ascribable to other causes

9. Occurrence of DCI during the ICU stay

DCI will be defined as the occurrence of

- Focal neurological deficit (such as hemiparesis, aphasia, apraxia, hemianopia, or neglect), or
- Decrease of at least 2 points on the Glasgow Coma Scale (either on the total score or on one of its components [eye, motor on either side, verbal]).

➤ for at least 1 hour,
 ➤ not apparent immediately after aneurysm occlusion, and
 ➤ cannot be attributed to other causes by means of clinical assessment, CT or MRI scanning of the brain, and appropriate laboratory studies

10. Occurrence of cerebral vasospasm on a brain imaging on digitally substracted angiography (DSA) or Magnetic resonance/computed tomography angiogram (MR/CTA) performed upon clinical signs of delayed cerebral ischemia or severe impairment of cerebral blood velocity in transcranial doppler

Cerebral Vasospasm diagnosis will be defined upon DSA or MR/CTA.

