On angiograms in DSA or MR/CTA, the severity of vasospasm will be considered none or mild if there is a less 33% decrease in arterial diameter on angiography, moderate if there is a 34% to 66% decrease, or severe if there is at least a 67% decrease.

DSA or MR/CTA will be performed when:

- There are signs of delayed cerebral ischemia as described above.
- There is a severe impairment of cerebral blood flow velocity assessed with help of transcranial doppler (tCD), as defined below. tCD will be performed at the discretion of the physicians in charge. tCD is a non-invasive radiation free exam that can be used at bedside. Its repetition allows a better detection of vasospasm and is routinely performed. Cerebral vasospasm severity will be evaluated according to this scale:

Degree of cerebral blood velocity alteration	Mean flow velocity (cm/s)	Lindegaard ratio
Mild	120-149	3-6
Moderate	150-199	3-6
Severe	>200	>6

11. Occurrence of new cerebral infarcts

New cerebral infarct is considered when detected on the CT scan or MRI performed with 6 weeks, (or on the latest CT scan or MRI performed before death within 6 weeks, or at autopsy), but not present on the earlier CT or MRI scan performed between 24 and 48 h after early aneurysm occlusion and not ascribable to other causes such as surgical clipping or endovascular treatment. Hypodensities on CT imaging resulting from ventricular catheter or intraparenchymal hematoma should not be considered cerebral infarctions secondary to DCI.

12. Occurrence of cilostazol-related major adverse events, including: arrhythmia, abnormal bleeding and allergy.
13. Occurrence of cilostazol-related minor adverse events include: tachycardia, fever, fainting, nausea, vomiting and stomach pain.

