5.2 Follow-up Visits

Follow up visits will be performed daily from day 1 to day 28. One Brain imaging will be realized 24/48 hours after the aneurism treatment and one between day 28 and 45 after randomization. Transcranial doppler, MR CTA or DSA results will be collected when realized.

Day 1 to day 28

Vital status

Compliance to treatment

Experimental Treatment administration will be collected daily

Safety follow up

- Any major Cilostazol-related adverse event will be assessed:
 - Arrhythmia from auricular origin
 - Arrhythmia from ventricular origin
 - Abnormal bleeding
 - Allergy
- Other minor Cilostazol-related adverse events:
 - Tachycardia,
 - Fever
 - Fainting
 - Nausea
 - Vomiting
 - Stomach pain

Cerebral vasospasm

- Blood flow velocity increase on TCD
- Cerebral vasospasm diagnosed upon MR/CTA or DSA and its severity (mild/moderate/severe)

Delayed cerebral ischemia

- New focal deficit
- Glasgow point decrease
- No other cause

Treatment in the last 24 hours

- Continuous sedation
- Mechanical ventilation
- Extraventricular drain
- Therapy Intensity Level (TIP) for Raised ICP treatment (See Appendix 7)
- Hypertension therapy
- Vasopressors (epinephrine/norepinephrine/dobutamine)
- Milrinone administration
- Endovascular treatment (Balloon therapy or vasodilatator administration)
- Other treatment
- At ICU discharge, the modified Rankin scale will be evaluated by a blinded research technician in case of lost to follow up.

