12 STATISTICAL ASPECTS

12.1 Description of statistical methods to be used including the timetable for the planned interim analyses

CASH is a multicentre, double-blinded, randomised, placebo-controlled, parallel-group superiority trial in adult, using an adaptive group-sequential design, to demonstrate that cilostazol plus nimodipine is safe and superior to nimodipine alone will improve modified Ranking Score (mRS) at six months.

Two interim analyses for futility and efficacy are planned.

Populations

For the statistical analysis, the following populations are defined:

Population	Description
Intent-To-Treat (ITT) Population	The ITT population will include all randomised participants. ITT participants will be analysed according to the randomised treatment, regardless of the actual treatment received. All efficacy analyses will be performed on the ITT population.
Per Protocol (PP) Population	The PP population will include all participants in the ITT with at least 80% of doses received to define adherence to treatment. The PP population will be used for supportive analyses of efficacy measures.
Safety Population (SP)	The SP will include all randomised participants who received at least one treatment (active or placebo). The SP will be analysed according to the actual treatment received. This population will be used for safety analyses.

Description of the statistical methods, including the timing of planned interim analyses

The statistical analysis plan (SAP) will be developed and finalised before the database is locked.

Below is a description of the planned statistical analysis. Further details will be presented in the statistical analysis plan (SAP).

All statistical analyses will be performed with SPSS version 26 or RStudio. For analyses performed with RStudio, the script used will be provided.

The baseline is defined as the last evaluation performed before the start of the study treatment, day 1 (V1).

All data collected after the start of the study treatment are defined as post-baseline.

Baseline characteristics will be summarised by the treatment group. The mean and standard deviation (SD) or median and interquartile range (IQR) for skewed variables will be summarised for continuous measures.

The proportion in each category will describe categorical variables.

In addition, the 95% confidence interval (CI) will also be calculated as indicated.

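### The DCI and new-infarct secondary endpoints are timed from aneurysm occlusion and never from randomisation, so some events that precede randomisation can count as outcomes

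*Protocol*

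**What the plan says.** The infarct endpoint (Protocol 3.2, 4.1.2 item 11, 5.3) counts a lesion found within six weeks if it was "not present on the earlier CT or MRI scan performed between 24 and 48 h after early aneurysm occlusion". Item 11 also removes lesions by cause: they must be "not ascribable to other causes such as surgical clipping or endovascular treatment".

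The DCI endpoint in 3.2 is a new focal deficit or a fall in the coma score "which does not occur immediately after aneurysm occlusion and which is not ascribable to other causes". Section 4.1.2 item 9 uses the same anchor, adds a one-hour minimum duration, and sets the observation window as "Occurrence of DCI during the ICU stay".

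On timing, 5.1 and 6.1 require the aneurysm to have been secured before inclusion. The synopsis (practical procedure) says of study drug: "This treatment should be started within the first 96 hours after hemorrhage". Section 5.2 schedules the early scan from the procedure ("One Brain imaging will be realized 24/48 hours after the aneurism treatment") and the late scan from randomisation. Daily recording, including DCI, runs from day 1 to day 28. Section 5.1 records recent ischaemia on imaging at inclusion or more than 6 h after aneurysm treatment.

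Section 9.3 gives the adjudication committee the final word on secondary endpoints and has it work from material stripped of dates.

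**The concern.** Occlusion always comes before randomisation, by an interval that the protocol does not fix. An endpoint whose clock starts at occlusion, and which never refers to randomisation, can pick up events that happened before the patient was allocated. Study drug cannot have prevented those events. They add the same expected number to each arm and pull the observed effect towards no difference. How many are added depends on how soon after occlusion each site randomises.

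These endpoints matter because 2.1 and 2.4 give prevention of DCI as the mechanism by which the drug should improve outcome. If they are blurred, the trial's evidence on mechanism is blurred too. The committee that could sort early from late events is not given the dates it would need.

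**Working it through.** The protocol states no event rate, effect or power for DCI or infarct in this trial, so there is no planned figure to reproduce. The check covers timing first, then an illustration of dilution.

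**Inputs**
- Occlusion precedes inclusion (5.1, 6.1); first dose by 96 h after the bleed (synopsis).
- Reference scan at s = 24 to 48 h after occlusion (3.2, 5.2).
- DCI risk begins at day 4 (2.4) and is mainly on days 4 to 10 (2.2).
- 28 tablets, one every 12 h for 14 days, or 336 h (7.1.1).
- Let t be hours from occlusion to randomisation, with the first dose assumed to follow at once. Then t lies between 0 and just under 96.

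**Pre-randomisation time that can contribute events**
- DCI: about t, so at most just under 96 h.
- Infarct: max(0, t − s). With s = 24 this is at most just under 96 − 24 = 72 h. It is zero whenever t is below 24 h.
- Example, t = 72 h: about 72 h for DCI; 72 − 48 = 24 h to 72 − 24 = 48 h for infarct.

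These are limits. The largest values need occlusion almost at the moment of the bleed and dosing at the last permitted hour. They also lie largely before the stated risk period. If the day of the bleed is day 0, day 4 starts at hour 96 and there is essentially no overlap. If it is day 1, day 4 starts at hour 72 and the overlap is at most 96 − 72 = 24 h.

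**The opposite order: scan after the first dose (infarct only)**
- On-treatment time before the scan: max(0, s − t), at most 48 h, or 4 of 28 tablets (48/336 = 14% of the course by the clock, not of events).
- The scan falls after hour 96 only if occlusion is later than 96 − 48 = 48 h after the bleed. With earlier occlusion, few delayed infarcts should be present on it.

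**Illustrative dilution, DCI.** Control rate 30% (2.2, stated there for survivors). True risk ratio 0.55, an assumption; the symptomatic-vasospasm ratios that follow from 2.3 are 22.4/37.3 = 0.60, 13/40 = 0.33 and 10.8/24.3 = 0.44. Let q be the assumed share of control events that precede randomisation. Active rate = 0.30q + 0.30(1 − q) × 0.55.

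| q | Active rate | Observed ratio | Difference (points) |
|---|---|---|---|
| 0 | 16.5% | 0.55 | 13.5 |
| 0.05 | 17.2% | 0.57 | 12.8 |
| 0.10 | 17.9% | 0.60 | 12.2 |
| 0.15 | 18.5% | 0.62 | 11.5 |

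**Illustrative dilution, infarct.** Observed ratio = q + (1 − q) × true ratio; power for 284 per arm, two-sided 0.05.
- Using 27.5% v 10.2% from one earlier trial in 2.3: q = 0, 0.05, 0.10 gives ratios 0.37, 0.40, 0.43 and power 1.00, 0.999, 0.997.
- Using 29% (another trial in 2.3) and an assumed true ratio of 0.70: ratios 0.70, 0.715, 0.73 and power 0.67, 0.63, 0.58.

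Dilution is immaterial if the effect is as large as in the first case, and noticeable if it is modest.

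**Do other provisions close the gap?** Daily recording from day 1 limits capture of earlier DCI, but a deficit that began between occlusion and randomisation and is still present on day 1 meets the definition. Section 6.2 does not exclude such patients. The committee, working without dates, cannot place an event before or after randomisation.

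**The case against.** The strongest reply is that the protocol already deals with most of this. Treatment is meant to start before the DCI risk period. Complications up to inclusion go on the inclusion form, daily DCI recording begins on day 1, and 12.1 calls data collected after the start of treatment post-baseline. A blinded committee has precedence, and counting windows are often left to a statistical analysis plan. The endpoints are items 9 and 11 of 13 secondary criteria.

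Much of that stands: it limits the size and confines the point to secondary endpoints. It does not remove the gap, because the endpoint definitions are fixed in this document and contain no rule that excludes onset before randomisation.

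Two stronger readings are tempting and are not supported.
- A reader might infer a contradiction with 12.1, which states: "The baseline is defined as the last evaluation performed before the start of the study treatment". That is a general baseline for summaries and change scores. A reference scan that separates early from delayed lesions serves another purpose and can coexist with it.
- A reader might infer that the 24-48 h scan should lose its power to exclude lesions because it can follow the first dose. Section 10.3.3.1 acknowledges that securing the aneurysm can itself cause ischaemic stroke, and this scan screens such lesions out objectively. No scan is scheduled between occlusion and randomisation to replace it. What remains is that exclusion by a post-dose scan conditions on something measured after randomisation and could differ by arm if the drug acts early. A sensitivity analysis addresses that.

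**Conclusion.** The point holds in a limited form. As written, DCI with onset before randomisation, and an infarct arising after the reference scan but before a late randomisation, can count as outcomes. The consequence is dilution, balanced between arms in expectation, and probably slight given the protocol's own timing of DCI risk. The hour figures are limits, because the protocol gives no distribution of occlusion-to-dose times. The dilution figures rest on assumed shares and, except for the infarct case taken from an earlier trial, on assumed effects; they illustrate scale only. The primary mRS endpoint, the 284 per arm and the total of 630 are unaffected. The wording should be corrected because the remedy is nearly free.

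**What to change.** In 3.2, 4.1.2 (items 9 and 11) and 5.3:
- Count DCI only if its onset is after randomisation, and keep every randomised patient in the denominator.
- Do not count an infarct already visible on any scan before randomisation, including the imaging recorded at inclusion under 5.1.
- Keep the 24-48 h scan as the reference for excluding procedural infarcts. Where it falls after the first dose, report a sensitivity analysis that also counts lesions first seen on it and not attributed to the procedure.

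In 9.3, supply the committee with the times of occlusion, scans, first dose and event onset relative to randomisation. Relative times need not reveal the allocation.

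The cost is a few timing fields and one extra analysis; no scan is added. The infarct rule works only where a pre-randomisation scan exists, so a lesion that arises after the last such scan and before randomisation will still be counted. The recorded times will show how often that was possible.
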